**Regulatory Agency Identifier Number(s): N/A**

## Version History

Version Number	Date	Type	Section	Change
1.0	04-Jun-2021	Initial release	N/A	N/A
1.1	30-Nov-2021	Local amendment: Only applicable for UK	N/A	No change for V2.3
1.2	21-Jan-2022	Local amendment: Only applicable for Spain	N/A	No change for V2.3
2.0	28-Feb-2022	Local Amendment  PMCF – provision of study devices: Changing study from Observational to Interventional; reduction minimum VAD Therapy period	
 
Header Section
 
Sponsor Protocol Approval
 
Throughout the document
 
Synopsis – Participants
 
Synopsis
 
Section 2.3.1 Risk Assessment
 
Section 2.3.2 Benefit Assessment
 
Section 2.3.3 Overall Benefit: Risk Conclusion
 
Section 5.1 Inclusion Criteria
 
	
 
Protocol Title: Change from “Observation” to “Post-Market Clinical Follow Up” Study
 
Change of Statistician
 
Reference to “observational” changed
 
Inclusion criterion 2: Expected minimum VAD therapy reduced from 7 to 3 days
 
Addition of anticipated study timelines
 
Adjustment of risk section to PMCF with interventional element
 
Adjustment of risk section to PMCF with interventional element, addition of clinical benefits
 
Adjustment of risk section to PMCF with interventional element
 
Inclusion criterion 2: Expected minimum VAD therapy reduced from 7 to 3 days
 
Information added
 
Information added
 

Version Number	Date	Type	Section	Change
			
 
Section 6.4 Device Labeling
 
Section 6.5 Treatment Allocation and measures to minimize bias
 
Section 7.1 Study duration
 
Section 9.1.1. Adverse Events
 
Section 11.5 Device accountability
 
Section 12.1 Control of Study products
 
	
 
Updated timelines
 
“Procedure” added to AE definition
 
Information added
 
Clarification that Sponsor will provide marketed products as study devices
 

V2.1	15-Mar 2022	Local amendment: Only applicable for BE	
 
N/A
 
	
 
Local Amendment BE01 – Not applicable for this version
 

V2.2	30-May 2022	Local amendment: Only applicable for ES01	
 
N/A
 
	
 
Local Amendment ES01 – Not applicable for this version
 

V2.3	13JUL2022	Local Amendment: Only applicable for ES02	
 
Sponsor Protocol Approval
 
Synopsis & Section 5.2 – Exclusion Criteria
 
	
 
Change of medical monitor, medical affairs representative, and statistician
 
Change of exclusion criterion 1 to allow for disinfecting cap placement within 12 hours prior to ICF signature
 

V2.4	11OCT2022	Local Amendment: Only applicable for ES02	
 
Sponsor Contact Details
 
Protocol
 
Section 7.1
 
	
 
Update of Clinical Project Manager
 
Update of Format
 
Updated timelines
 

Version Number	Date	Type	Section	Change
V2.5	01DEC2022	Local Amendment: Only applicable for AT01	

• Abbreviations

• Inclusion criteria (Synopsis & Section 5.1)

• Synopsis

	

• Update on Abbreviations

• For AT01 LAR is not applicable

• Update on Timelines & Investigational Sites

## Abbreviations

ADE	Adverse Device Effect
AE	Adverse event
BD	Becton Dickinson and Company
BSI	Blood Stream Infection
CE	Certification Mark
CI	Confidence Interval
CLABSI	Central Line Associated Blood Stream Infection Defined as a primary BSI with use of a central vascular catheter in the 48 hours (two days) before the onset of the infection
CRBSI	Catheter-related Bloodstream Infection Defined as the presence of bacteraemia originating from an intravenous catheter 
CSA	Clinical Study Agreement
CV	Curriculum Vitae
DEHP	Diethylhexyl Phthalate
DMP	Data Management Plan
eCRF	Electronic Case Report/Record Form
EEA	European Economic Area
EU	European Union
FDA	Food and Drug Administration
FDAAA	FDA Amendments Act of 2007
GCP	Good Clinical Practice
GDPR	General Data Protection Regulation
ICF	Informed Consent Form
ICH	International Conference on Harmonisation
ICMJE	International Committee of Medical Journal Editors
IFU	Instructions for Use
IPA	Isopropyl Alcohol
IRB/EC	Institutional or Independent Review Board/Ethics Committee
IV	Intravenous
LAR	Legal Authorized Representative
NDA	Non-disclosure Agreement
PI	Principal Investigator
SADE	Serious Adverse Device Effect
SAE	Serious Adverse Event
SIV	Site Initiation Visit
TMF	Trial Master File
UADE	Unexpected Adverse Device Effect
USADE	Unexpected Serious Adverse Device Effect
VAD	Vascular Access Device

## 1 PROTOCOL SUMMARY

[figure not shown]
### 1.1 Synopsis

Protocol Title	A Post-Market Clinical Follow Up Study to Evaluate BD PureHub™ Disinfecting Cap Use on Needle-Free Connectors	
Rationale	This study is designed to provide data utilizing the Becton Dickinson (BD) PureHub™ Disinfecting Cap for the purpose of providing clinical data required under European Union (EU) regulation 2017/745.	
Objectives and Endpoints	Objectives	Endpoints
Primary Efficacy Objective		

■ Attachment success rate of the BD PureHub™ Disinfecting Caps to a needle-free connector (successful attachment/ total number of attachments)

■ Removal success rate of the BD PureHub™ Disinfecting Caps to a needle-free connector (successful removal/ total number of intended removals)

Primary Safety Objective		

■ Rate of device-related adverse events

Informative Objectives		

■ The number of BD PureHub™ Disinfecting Caps used per day/per study participant

■ The purpose for each intended removal of the BD PureHub™ Disinfecting Cap from the needle-free connector

■ Incidence of central line associated bloodstream infection (CLABSI)

■ Incidence of bloodstream infections

Protocol Title	A Post-Market Clinical Follow Up Study to Evaluate BD PureHub™ Disinfecting Cap Use on Needle-Free Connectors
Design and Overview	
A Post-Market Clinical Follow Up Study to Evaluate BD PureHub™ Disinfecting Cap Use on Needle-Free Connectors:
 
This is a multi-center, prospective observational study of a minimum of 150 study participants who have vascular access devices (VADs) with needle-free connectors as part of their routine medical care.
 
Patients will be followed from the time of enrollment through the duration of one week post VAD therapy, department/ hospital discharge if VAD therapy has ended, or 45 days post enrollment date, whichever comes first.

Study Device	
BD PureHub™ Disinfecting Cap is comprised of a threaded plastic cap containing a porous pad pre-saturated with 70% Isopropyl Alcohol (IPA) and sealed with a multilayer foil film.
 
BD PureHub™ Disinfecting Caps are intended to be used as a disinfecting device for swabbable needle-free luer connectors prior to access and to act as a physical barrier between line accesses.

Participants	
Inclusion Criteria:
 

1. Has an eligible vascular access device with needle-free connectors in situ or will have one placed Note: This covers all needle-free devices, including central venous catheters, peripheral IV catheters and arterial VADs

2. Is expected to receive VAD therapy for a minimum of 3 days

3. Is expected to be available for regular observation from consent until end of study

4. Able and willing to provide informed consent or legal authorized representative (LAR)* authorized to give consent on behalf of the participant

 
*LAR not applicable for AT01
 
Exclusion Criteria:
 

1. BD PureHub™ Disinfecting Cap or any other disinfecting cap in place for more than twelve (12) hours (>12 hours) prior to study participation

2. Presence of any infection, bacteremia, or septicemia is known or suspected

3. Any condition which, in the opinion of the Investigator, precludes the participant from participation in this study

Protocol Title	A Post-Market Clinical Follow Up Study to Evaluate BD PureHub™ Disinfecting Cap Use on Needle-Free Connectors
Intervention(s)/Procedure(s)	The BD PureHub™ Disinfecting Cap will be used for needle-free access of the vascular access device as necessary for each participant from enrollment through one week post VAD therapy, department/ hospital discharge if VAD therapy has ended, or 45 days post enrollment date, whichever comes first. During this time, attachment and removal success will be captured, as well as any device-related adverse events (AEs).
Investigational Sites	Up to 10 sites in the EU will participate in this study.
Data Monitoring Committee	A Data Monitoring Committee will not be used in this study.
Regulatory Status	The BD PureHub™ Disinfecting Cap is currently CE marked and marketed in the EEA under CE certificate 252.1127, CE mark #0050.
Anticipated Study Timelines	The enrollment of the study started on 31JAN2022. Last participant will leave the study approximately in Q2 2023.

## Schema

*Table 1 – Schedule of activities*

Procedure/Assessment	Baseline	Initial PureHub Placement  Day 0	Each day during VAD Therapy 	7-day Follow Up after VAD Therapy 	End-of-study 45-day FU or Department/ Hospital Discharge, whichever comes first 
Informed consent process, incl. Informed consent signature date	X				
Inclusion/Exclusion Criteria Check	X				
Patient in-hospital location information	X	(X) 	(X) 	(X) 	
Demographics	X				
Medical History	X				
VAD Information 	X	(X) 	X		
BD PureHub™ Placement Record number of eligible needle-free connectors per VAD • Placement of PureHub™ Caps • Record number of new caps used and location catheter line per day incl. primary reason for cap replacement • Document Yes or No if able to successfully attach a PureHub™ Disinfecting Cap per needle-free connector for each attachment. • Document number of attachments • Document Yes or No if able to successfully remove the BD PureHub™ Disinfecting Cap from the needle-free connector • Document number of intended removals		X	X		X
Device related Adverse Events assessment		X	X	X	X
Blood stream infection assessment		X	X	X	X
Device deficiency assessment		X	X		

- 1) Initial PureHub™ Placement can be performed on same day as Baseline, provided ICF has been signed.
- 2) Multiple Placements of PureHub™ Caps are possible per day
- 3) VAD Information: At baseline -VAD type, number of VADs, number of lumens per catheter, location of VADs, date of VAD placement, type and number of needle-free connectors per VAD, type of dressing; subsequent visits; type of dressing in case of changes, dressing changes, needle-free connector changes,
- 4) Only applicable for patients who continue to be hospitalized at the department/hospital and continue study participation
- 5) End of study is also applicable if the patient is discharged from department and cannot be followed up by the clinical investigation team at another department/ward
- 6) Baseline VAD Information at initial PureHub™ Placement day needs to be reconfirmed if the visit date is different to baseline date
- 7) Only in case participant is transferred to another department/ward and continues in the study, or participant is discharged home in-between hospital visits but the VAD is still in place.

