## 4 STUDY DESIGN

### 4.1 Overall Design

This is a multi-center, single-arm, prospective post-market study that will enroll up to 175 participants in order to have 150 evaluable participants who have vascular access devices as part of their routine medical care. Data related to the safety and performance of the BD PureHub™ Disinfecting Cap will be captured when used as intended.

Participants will be screened against eligibility criteria and will be considered enrolled once the informed consent document is signed. Each study participant will have a BD PureHub™ Disinfecting Cap attached to each eligible needle-free connector to one or more VADs by a clinician. Clinicians will then be advised to place subsequent BD PureHub™ Disinfecting Caps as per the Instructions for Use through the course of the participant's IV therapy. During this time, attachment and removal success will be captured, as well as any device-related adverse events (AEs).

Participants will be followed from the time of enrollment until one week post VAD therapy, department/hospital discharge or 45 days post enrollment date, whichever comes first. Participants, with a VAD in place, who will be discharged from the hospital, but return regularly for catheter access to the site will remain in the study, either until the 45 days are reached or the VAD therapy is ended. If the catheter access will not be performed at the clinical trial site, the participant cannot continue in the study.

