### 4.3 End of Study Definition

A participant is considered to have completed the study when one of the following conditions are met, whichever is the earliest.:

- upon one week post VAD therapy (after the last VAD is removed),
- at department discharge provided the clinical investigation team cannot follow-up the participant on another ward for study purposes,
- at hospital discharge provided participant, if VAD is still placed, will not return for catheter access to the site or,
- 45 days from enrollment

If a participant has more than one (1) VAD with eligible needle-free connectors at study start, data will be collected on each VAD and the end of study time point occurs when the last VAD is removed. If an additional VAD is placed at a later time point, or if one of these VADs is replaced, then the new VAD is excluded from the study.

The end of the study is defined as the date of the last study assessment of the last participant in the study.

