2.1 Study Design

This is a multi-center, single-arm, prospective post-market study that will enroll up to 175 participants in order to have 150 evaluable participants who have vascular access devices as part of their routine medical care. Data related to the safety and performance of the BD PureHub™ Disinfecting Cap will be captured when used as intended.

Participants will be screened against eligibility criteria and will be considered enrolled once the informed consent document is signed. Each study participant will have a BD PureHub™ Disinfecting Cap attached to each eligible needle-free connector to one or more VADs by a clinician. Clinicians will then be advised to place subsequent BD PureHub™ Disinfecting Caps as per the Instructions for Use through the course of the participant's IV therapy. During this time, attachment and removal success will be captured, as well as any device-related adverse events (AEs).

Participants will be followed from the time of enrollment until one week post VAD therapy, department/hospital discharge or 45 days post enrollment date, whichever comes first. Participants, with a VAD in place, who will be discharged from the hospital, but return regularly for catheter access to the site will remain in the study, either until the 45 days are reached or the VAD therapy is ended. If the catheter access will not be performed at the clinical trial site, the participant cannot continue in the study.

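### BSI and adverse-event surveillance after VAD removal depends on staying in hospital, so some central-line participants leave before the protocol's own 48-hour CLABSI window closes

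*Protocol*

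**What the plan says.** The protocol's abbreviation list defines CLABSI as a primary BSI with "use of a central vascular catheter in the 48 hours (two days) before the onset of the infection". Table 1 has a column for a 7-day check after VAD therapy, with device-related adverse events and BSI both marked. Footnote 4 restricts that column: "Only applicable for patients who continue to be hospitalized at the department/hospital and continue study participation".

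The rules for when observation stops are spread over several places:

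- Synopsis: follow-up runs to "one week post VAD therapy, department/ hospital discharge if VAD therapy has ended, or 45 days post enrollment date, whichever comes first".
- Protocol 4.1: "one week post VAD therapy, department/hospital discharge or 45 days post enrollment date, whichever comes first", here without the condition that VAD therapy is over. SAP 2.1 has the same rule.
- Protocol 4.1, participants sent home with a VAD who return to the site for access: they "will remain in the study, either until the 45 days are reached or the VAD therapy is ended".
- Protocol 4.3: participation ends at the earliest of several conditions, among them "upon one week post VAD therapy (after the last VAD is removed") and "at hospital discharge provided participant, if VAD is still placed, will not return for catheter access to the site". The same section then says that, for participants who start with more than one VAD, the end comes when the last one is taken out.
- Protocol 7.6 stops capture of device-related adverse events when participation ends. Protocol 8.2 sets loss to follow-up aside because participants are said to be in hospital throughout.

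SAP 5.2 divides participants with a device-related adverse event by all participants in the enrolled population. SAP 5.3 summarises BSI and CLABSI as counts and percentages in the evaluable population. Neither uses person-time or takes account of how long each participant was observed after removal.

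**The concern.** BSI is one of only two classes of event that the study collects (Protocol 9.1.1), and the sponsor thought the week after removal worth a scheduled check. Whether a participant gets that check depends on whether they are still in hospital. A participant discharged on the day the line comes out has no post-removal observation. Under Protocol 4.3 that participant has nevertheless completed the study, and under the SAP counts as free of events.

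An infection that starts at home and is treated elsewhere, or on readmission after study exit, does not enter the numerator, while the participant stays in the denominator. The error runs in one direction: unseen events can only lower the reported BSI and CLABSI percentages. The result would be read as incidence over line use and its aftermath, when for some participants it is incidence up to discharge.

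**Working it through.** **1. The plan's own figure.** Protocol 10.2 and SAP 2.4 give the chance of seeing at least one event in 150 participants as 78% at a 1% rate and 95% at a 2% rate. With 1 − (1 − p)^150, p = 0.01 gives 77.9% and p = 0.02 gives 95.2%, so both reproduce. They hold for events that start under observation. If a share u of events starts after exit, p becomes p(1 − u):

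- u = 20%: 1 − (1 − 0.008)^150 = 70.0% and 1 − (1 − 0.016)^150 = 91.1%.
- u = 40%: 1 − (1 − 0.006)^150 = 59.5% and 1 − (1 − 0.012)^150 = 83.6%.

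The value of u is assumed; the documents do not give it.

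**2. One inpatient with one central line.** Take removal as the end of catheter use. The CLABSI window closes 48 hours later. If discharge comes h hours after removal, the unobserved part is 48 − h hours when h is below 48, and nothing otherwise. Discharge between 48 hours and 7 days leaves the CLABSI window complete but gives a shorter general BSI and adverse-event follow-up than a participant who stays. Peripheral and arterial VADs, which are also eligible (Protocol 5.1), have no 48-hour CLABSI window; only the general follow-up is shortened.

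**3. Share of the CLABSI window lost.** Assume a central line in place for d study days, discharge on the day of removal, and a flat hazard over d + 2 days. The unobserved share is 2/(d + 2). If only a fraction f of central-line participants leaves that way, the average loss is f × 2/(d + 2). The documents do not give f, so a range is shown.

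| Line days d | 2/(d + 2), f = 100% | f = 50% | f = 25% |
|---|---|---|---|
| 3 | 2/5 = 40% | 20% | 10% |
| 7 | 2/9 = 22% | 11% | 5.6% |
| 14 | 2/16 = 12.5% | 6.3% | 3.1% |

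Three days is the minimum expected VAD therapy in inclusion criterion 2, so the first row is the short end of the range.

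**4. Outpatients.** Set side by side, the passages do not agree.

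- Protocol 4.1 ends participation when VAD therapy ends or at day 45, and footnote 4 gives no 7-day check to someone at home. Together they leave no post-removal period.
- Protocol 4.3 lists one week after the last removal with no inpatient condition, and does not end participation at discharge for someone who returns for access. That reading gives a week.
- Protocol 4.3 also ends the study at the last removal for participants with several VADs, which again gives none.
- Protocol 8.2 assumes that nobody is an outpatient, against Protocol 4.1 and Table 1 footnote 7.

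**5. The 45-day cap.** Since 45 − 7 = 38, anyone whose last VAD is removed after day 38 loses part of the week, even in hospital. This follows from the cap, not from discharge.

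**The case against.** The best defence is that the stopping rule is openly stated as the earliest of three events. One week is then an upper limit, and incidence to study exit is a defined quantity. BSI and CLABSI are informational, there is no comparator, and SAP 2.8 sets no acceptance criteria. BSI and adverse events are assessed at discharge itself. All of this stands, and it limits how serious the point is. It does not answer the mismatch with the protocol's own 48-hour definition, nor the absence of any statement in the SAP that the percentages stop at exit. SAP 6.5 promises a follow-up visit summary, but does not say what it will contain and does not change the estimator.

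Four stronger readings are tempting, and the documents do not support them.

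- A reader might infer that every outpatient leaves before the CLABSI window closes. Protocol 4.3 can be read the other way, and outpatients who reach day 45 with the VAD in place exit through the cap. What is shown is a contradiction.
- A reader might compute 7/(d + 7), which is 70%, 50% and 33% for 3-, 7- and 14-day lines, as the share of intended follow-up lost. The plan did not promise the full week to discharged participants.
- A reader might treat removal on the day of discharge as typical, or lost time as lost events. The documents give no discharge timing, and the hazard may fall once the line is out.
- A reader might conclude that the primary device-related adverse-event rate is biased. Only events judged related or likely related, with onset after exit, could affect it. Protocol 9.3 asks for a reasonable or plausible time relation to cap use, and most risks listed in 2.3.1 concern the cap while it is handled or in place. Bias there is possible but not shown.

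**Conclusion.** The concern holds in a limited form. Post-removal surveillance depends on remaining in hospital. Central-line participants discharged within 48 hours of removal leave with the CLABSI window open, and anyone discharged within 7 days is observed for less time than someone who stays. With crude proportions, any resulting error in BSI and CLABSI incidence is downward.

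Its size cannot be derived from the documents. The 40%, 22% and 12.5% figures are shares of observation time for the participants affected. They rest on a central line, same-day discharge, removal as the end of use, and a flat hazard. For outpatients, the finding is that the protocol's passages must be reconciled. Because the endpoints are informational and no decision rule depends on them, this is worth correcting but does not undermine the study's primary performance results.

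**What to change.** Add one record check or telephone contact by existing site staff, for BSI and device-related adverse events, at day 7 after removal of the last study VAD (or day 45 if earlier). It applies to participants who leave with the VAD removed, not to those who withdraw. Reconcile Table 1 footnote 4, the synopsis, Protocol 4.1, 4.3, 7.6 and 8.2, and SAP 2.1 and 2.6 with that rule. Changing only some of them would create new contradictions. State explicitly what happens to outpatients and to participants with several VADs.

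The cost is at most one brief contact per discharged participant (no more than 175 are to be enrolled), submission of the amendment to the ethics committees with possible consent changes (Protocol 14.1), and perhaps slightly less favourable rates.

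If this is not adopted, change SAP 5.2 and 5.3 only:

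- Report how many participants have complete 48-hour (central line) and complete 7-day post-removal observation. The VAD removal and end-of-study dates are already used in SAP 5.3.
- Give BSI and CLABSI rates per VAD-day or observed person-day beside the crude proportion. Observed person-days reflect unequal follow-up directly; neither denominator recovers unseen events.
- Label the crude figure *incidence to study exit*.

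Do not present the rate in the fully observed subset as the corrected estimate. A BSI can itself prolong the stay, so that subset is partly selected on the outcome. This version costs one extra table and some labelling.
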